6.0 Inclusion and Exclusion Criteria

6.1 Describe the criteria that define who will be **included** in your final study sample.

NOTE: This may be done in bullet point fashion.

Response:

- 1) Type 1 Diabetes on continuous subcutaneous insulin infusion (CSII; also known as insulin pump) or multiple (four or more) injections of insulin per day.
- 2) Using a continuous glucose monitoring device (CGM) or regularly measuring their blood sugars four times daily.
- 3) HbA1c of less than 10.0%.
- 4) Well versed with carbohydrate counting.
- 5) Age 18-80 years
- 6) $BMI \geq 25 \text{ kg/m}^2$
- 7) Age at diagnosis of type 1 diabetes should be <30 years.
- 8) Evidence of auto-immunity to beta cells (GAD-65 and islet cell antibody screen)

6.2 Describe the criteria that define who will be **excluded** from your final study sample.

NOTE: This may be done in bullet point fashion.

Response: 1) Type 1 diabetes for less than 6 months;
2) Coronary event or procedure (myocardial infarction, unstable angina, coronary artery bypass, surgery or coronary angioplasty) in the previous four weeks;
3) Hepatic disease (transaminase > 3 times normal) or cirrhosis;
4) Renal impairment (serum eGFR $<30 \text{ ml/min/1.73m}^2$);
5) HIV or Hepatitis B or C positive status;
6) Participation in any other concurrent clinical trial;
7) Any other life-threatening, non-cardiac disease;
8) Use of an investigational agent or therapeutic regimen within 30 days of study.
9) history of pancreatitis
10) pregnancy
11) inability to give informed consent
12) history of gastroparesis

- 13) history of medullary thyroid carcinoma or MEN 2 syndrome.
- 15) Use of any agent other than insulin for treatment of diabetes (metformin, pramlintide or thiazolidinediones;
- 16) painful gallstones;
- 17) alcoholism;
- 18) hypertriglyceridemia (>500 mg/dl)
- 19) History of pancreatitis

6.3 Indicate specifically whether you will include any of the following special populations in your study using the checkboxes below.

NOTE: Members of special populations may not be targeted for enrollment in your study unless you indicate this in your inclusion criteria.

Response: None of the below populations will be enrolled

- Adults unable to consent
- Individuals who are not yet adults (infants, children, teenagers)
- Pregnant women
- Prisoners

6.4 Indicate whether you will include non-English speaking individuals in your study. **Provide justification if you will exclude non-English speaking individuals.**

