Study Visit day 0: Subjects will come fasting for this visit. Each subject will be given one injection of Liraglutide 1.2 mg or placebo. A fructosamine and blood samples will be collected at baseline. Blood samples will be collected after the baseline at 30, 60, 120, 180, 240 and 300 minutes after the injection. (**This is being done to evaluate the acute effect of a single injection of Liraglutide on oxidative stress and inflammatory mediators, before any adjustments of insulin dose or effect of Liraglutide on blood glucose and weight is evident**). Subjects will be instructed by the study staff in the dosing and administration of the study medication. They will start Liraglutide injection at a dose of 0.6 mg per day or placebo injection on the following day. We will adjust the doses of basal and bolus insulin to eliminate low blood sugars(less than 70 mg/dl). At all subsequent visits insulin doses will be titrated to target blood sugars between 70-180 mg/dl at all times. Patients will return to the center after 7 days.

Study Visit week 1: Blood glucose concentrations will be reviewed. Insulin dose will be adjusted at the discretion of the study investigator to optimize blood sugar control as per

the targets mentioned above. Patients will be advised to increase the Liraglutide dose to 1.2 mg a day if they are able to tolerate the 0.6 mg dose. If they are experiencing mild nausea, subjects will continue with 0.6 mg daily for another 7 days. Those with severe nausea/vomiting will be dropped from the study. All other subjects will return in 7 days.

Study Visit week 2: Blood glucose concentrations will be reviewed. Insulin dose will be adjusted if needed. Subjects taking 0.6 mg dose and experiencing significant nausea will be dropped from the study. Subjects on 1.2 mg and experiencing significant nausea will decrease the dose to 0.6 mg and continue that dose for the duration of the study. Subjects on 1.2mg and experiencing mild nausea will continue on 1.2 mg for 2 more weeks. Subjects on Liraglutide 1.2mg daily without any gastro-intestinal side-effects will be asked to increase the dose to 1.8 mg daily. Study drug will be dispensed for additional 2 weeks.

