Study Visit week 4: Subjects will be asked to bring in their used study pens and the pen that they are using so that study nurse can log in the amount of drug used. If needed, the dose will be increased. The goal in the first 4 weeks is to increase patient's liraglutide dose to maximum tolerated dose. Maximum dose of liraglutide will be 1.8 mg daily. Subjects experiencing mild nausea with 0.6 mg or 1.2 mg will continue at that dose in the study. Those with severe nausea/vomiting with 1.8mg will decrease their dose to 1.2 mg and continue that dose throughout the study. Blood glucose concentrations will be reviewed. Insulin dose will be adjusted if needed. CGM will be discontinued. Study drug will be dispensed to last till the next visit.

Study visit week 8: Subjects will be asked to bring in their used study pens and the pen that they are using so that study nurse can log in the amount of drug used. Blood glucose concentrations will be reviewed. Insulin dose will be adjusted if needed. Study drug will be dispensed to last till the next visit.

Study Visit week 12: Subjects will be asked to bring in their used study pens and the pen that they are using so that study nurse can log in the amount of drug used. Blood glucose concentrations will be reviewed and vascular activity will be performed. Insulin dose will be adjusted if needed. Fasting blood, research labs, HbA1c, fructosamine, lipid panel, urine pregnancy test and 24 hr urine will be collected. FMD and 24hr blood pressure will be studied. Study drug will be dispensed for additional 4 weeks.

Study Visit week 16 and 20: Subjects will be asked to bring in their used study pens and the pen that they are using so that study nurse can log in the amount of drug used. Blood glucose concentrations will be reviewed. Insulin dose will be adjusted if needed. Study drug will be dispensed for additional 4 weeks.

Study visit week 24: CGM will be inserted. They will have their body composition measured by DEXA and MRI prior to next visit.

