17.0 Data Management and Analysis

17.1 Describe the data analysis plan, including any statistical procedures. This section applies to both quantitative and qualitative analysis.

Response: The focus of the proposed research is to evaluate the effect of liraglutide on mean HbA1c% over the period of 26 weeks of treatment. The similarities between the study groups, baseline values for subject's demographics and study endpoints will be compared using appropriate parametric tests. Transformations of the data in order to meet statistical assumptions may be considered. The **primary endpoint** of the study is to detect

a difference in HbA1c after 26 weeks of treatment with Liraglutide or placebo. The statistical analysis will be carried out using analysis of covariance (ANCOVA) and tested at the 0.05 level. Change in weight will be a covariate. The results will be computed as mean \pm SD. Analysis will be carried out on the basis of intention to treat (with last observation carried forward).

The secondary end points based on glycemic changes will include the difference from baseline in mean weekly glucose concentrations, standard deviations of the mean weekly glucose concentrations, HbA1c, fructosamine, the duration of time spent in hyperglycemia ($>150\text{mg/dl}$, $>200\text{mg/dl}$, $>250\text{mg/dl}$) and hypoglycemia ($<70\text{mg/dl}$, $<40\text{mg/dl}$), insulin dosage. A reduction in the AUC following the meal will constitute another secondary end point. Between groups comparisons of the magnitude of change from baseline will also be made for these glycemia related secondary endpoints using student's t-test. Comparisons for these and the primary endpoints will also be made using the paired t-test or Wilcoxon's test for paired data within each group.

The other secondary end-points of the study will be change from baseline after 26 weeks of treatment in the fasting and postprandial blood sugars, glucagon and C-peptide concentrations, indices of oxidative and inflammatory stress in MNC, plasma and adipose tissue; subcutaneous fat mass, hepatic fat content and visceral fat mass; features of metabolic syndrome; gastric emptying, blood pressure, vascular analysis, patient reported nausea, quality of life and depression scores. Between groups comparisons will be made using students t-test or ANCOVA (adjustment will be done for baseline differences). Within group comparisons for these endpoints will be made using paired t-test or Wilcoxon's test or ANCOVA.

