17.2 If applicable, provide a power analysis.

NOTE: This may not apply to certain types of studies, including chart/records reviews, survey studies, or observational studies. This question is asked to elicit whether the investigator has an adequate sample size to achieve the study objectives and justify a conclusion.

Response: There are no prior randomized controlled trials that have examined the effect of Liraglutide on HbA1c in subjects with type 1 diabetes. In our observational study (preliminary data), we found a decrease in HbA1c of 0.35% after 6 months of liraglutide in patients with type 1 diabetes who had a mean HbA1c of $6.45\pm0.5\%$. In our proposed study, we will include patients with HbA1c up to 8.5%. Thus we expect a greater difference in HbA1c among the two groups at the end of the study. Conservatively estimating a difference in HbA1c of 0.35% between the two groups, a sample size of 32 patients per treatment group should provide 80% power to detect a significant difference ($\alpha = 0.05$), provided the standard deviation of the residuals is not greater than 0.5. Thus 64 subjects will be needed for the study. To account for a dropout rate of 30%, we will recruit 84 subjects into the study.

17.3 Describe any procedures that will be used for quality control of collected data.

Response: Three investigators and research nurse will double check the accuracy of collected data. All laboratory testing will be standardized using references and standards.

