20.0 Withdrawal of Subjects

N/A: This study is not enrolling subjects. This section does not apply.

20.1 Describe **anticipated** circumstances under which subjects may be withdrawn from the research without their consent.

Response: Pregnancy, DKA, severe and frequent hypoglycemia and drug intolerance (severe nausea and/or vomiting) developing any of the exclusionary condition listed in the inclusion and exclusion criteria.

The principal investigator of the study can remove a participant from the research study without their approval if for any reason he/she feels is appropriate, including: severe side effect, injury or medical condition which may place the patient at risk of further complications if patient continues to participate, failure to take the medication as instructed, failure to keep your scheduled appointments, cancellation of the study by the sponsor, or other administrative reasons.

Participation in this research study is voluntary. Subjects have the right to refuse to participate or to withdraw from participation at any time for any reason. Refusal to participate or withdrawal from the study will involve no penalty or loss of entitled benefits, nor affect the subjects ongoing medical care

20.2 Describe any procedures for orderly termination.

NOTE: Examples may include return of study drug, exit interview with clinician. Include whether additional follow up is recommended for safety reasons for physical or emotional health.

Response: If a subject withdraws from the research, the data collected to that point will be used toward the research finding. If applicable the subject will have to bring back any unused research drug and or device. If necessary, they will be asked to complete an end of study visit for their safety.

20.3 Describe procedures that will be followed when subjects withdraw from the research, including retention of already collected data, and partial withdrawal from procedures with continued data collection, as applicable.

Response: If a subject withdraws from the research, the data collected to that point will be used toward the research finding. Patients are allowed to withdraw from some procedures while continuing to participate in the study (take study medication). Efficacy and safety data will continue to be collected for the parts of study that patients agree to participate in.

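### 84 randomised with 30% dropout leaves about 59 completers, not the 64 on which section 17.2 bases its 80% power; the HbA1c limits in 17.2 and 6.1 also differ

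*Combined protocol and SAP*

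**What the plan says.** Section 17.2 takes a difference of 0.35 percentage points in HbA1c, a residual SD no greater than 0.5 and alpha 0.05, and concludes that "a sample size of 32 patients per treatment group should provide 80% power to detect a significant difference", so 64 in total. It then adds: "To account for a dropout rate of 30%, we will recruit 84 subjects into the study". Sections 4.1, 5.1 and 11.2 repeat 84, and 4.1 and 11.2 split it as 42 per arm, so the figure is not a misprint.

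Section 17.1 describes a different handling of dropouts for the primary ANCOVA: "Analysis will be carried out on the basis of intention to treat (with last observation carried forward").

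Section 10.1 schedules HbA1c at screening, at week 12 ("Fasting blood, research labs, HbA1c, fructosamine, lipid panel, urine pregnancy test and 24 hr urine will be collected") and at week 26. At the week 1 visit it says: "Those with severe nausea/vomiting will be dropped from the study". It also drops some patients for nausea at week 2. For patients who withdraw, section 20.2 says: "If necessary, they will be asked to complete an end of study visit for their safety". It does not list the tests done at that visit.

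On the population, section 17.2 says "In our proposed study, we will include patients with HbA1c up to 8.5" percent, while the inclusion criterion in section 6.1 reads "HbA1c of less than 10.0" percent.

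**The concern.** If 30% of patients are lost, the number left is the number randomised times 0.70. Applied to 84, that does not return the 64 that 17.2 requires. The stated pairing of 80% power with 30% dropout is therefore not what 84 patients deliver on the section's own reasoning.

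There is a second difficulty. Section 17.2 inflates for dropout, which treats dropouts as lost to the analysis, whereas 17.1 keeps them in by carrying values forward. A reader cannot tell which analysis the 80% describes. Section 17.2 is the only justification of the sample size, so this affects how a null or borderline HbA1c result would be read.

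The HbA1c limit is a separate consistency point. Section 17.2 uses the 8.5% range to argue that the true effect should exceed 0.35, but the entry criterion admits a wider range.

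**Working it through.** **Inputs.** From 17.2: difference 0.35, residual SD 0.5, 32 per arm, 30% dropout, 84 recruited. From 17.1: alpha 0.05. From 4.1: 42 per arm. Sidedness is not stated; two-sided is assumed because it reproduces the plan's figure (one-sided would need about 26 per arm).

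**1. Reproduce the plan's 32 per arm.** n per arm = 2 × [(1.960 + 0.8416) × 0.5/0.35]² = 32.04. Power at 32 per arm is 80.0% by the normal approximation and 78.7% by the noncentral t. The 32 is sound, to rounding.

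**2. Check the dropout step.**
- Left after 30% loss: 84 × 0.70 = 58.8, or 29.4 per arm.
- Needed to keep 64: 64/0.70 = 91.4, so 92 (46 per arm).
- Loss that 84 can absorb: (84 − 64)/84 = 23.8%.
- The figure 84 agrees with 64 × 1.30 = 83.2 rounded up. No formula is stated, so this origin is an inference.

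**3. Power in completers.** Power ≈ Φ(0.35/[0.5 × √(2/n)] − 1.960).

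| Completers per arm | Normal | t |
|---|---|---|
| 32 | 80.0% | 78.7% |
| 29.4 | 76.5% | 75.1% |
| 29 | 76.0% | 74.5% |

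At 29 per arm, 80% returns (normal approximation) if the difference is 0.368 at SD 0.5, or if the SD is 0.476 at difference 0.35.

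**4. Power under the planned analysis (illustration only).** The documents do not fix this. Assume 42 per arm analysed, completer SD 0.5, 30% dropout in each arm, and a share q of all patients who carry baseline forward (zero change); the remaining dropouts are assumed to behave like completers. The mean difference is then (1 − q) × 0.35. The variance in an arm with mean completer change m is (1 − q) × 0.25 + q(1 − q)m². Normal approximation:

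| q | Placebo change 0 | −0.2 | −0.4 |
|---|---|---|---|
| 0 | 89.4% | 89.4% | 89.4% |
| 0.15 (half of dropouts) | 82.8% | 80.4% | 76.5% |
| 0.30 (all dropouts) | 73.6% | 68.6% | 61.1% |

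Both q and the placebo change are assumptions. A patient dropped at week 1 or 2 has no scheduled HbA1c after screening unless the optional end of study visit includes one, so q above zero is plausible, but its value is unknown.

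**5. HbA1c limits.** Up to 8.5% (17.2) and less than 10.0% (6.1) cannot both describe the enrolled population. The discrepancy alters none of the figures in steps 1 to 4, which use the plan's stated difference and SD.

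**The case against.** The strongest reply is that no completers analysis is planned. Section 17.1 specifies intention to treat with carried-forward values, and section 20.3 says that data collected before withdrawal will be used. If all 84 are analysed and the full 0.35 effect holds at SD 0.5, power is about 89%. The illustration gives less than 80% only under assumptions that the documents do not supply: at q = 0.10 it is 85.2% with no placebo change and 81.2% with −0.4. Underpowering of the primary test is therefore not shown. That stands, and it is why the 76% is confined to completers. It does not rescue 17.2: a section that inflates for dropout counts dropouts as lost, and on that footing its arithmetic is wrong. If dropouts count in full, no inflation is needed and 84 has no stated basis.

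A second reply is that the loss is small beside the uncertainty in the inputs. The 0.35 matches the before-and-after change in eight patients in the uncontrolled preliminary series, and the residual SD matters more: at an assumed SD of 0.6 or 0.7, 32 per arm gives about 65% or 52%. That is also fair. It limits the weight of the point but does not make the stated figure correct. The wider entry range could affect that SD, which is a further reason to reconcile the two limits.

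The choice between 29 per arm and 59 in total (29 + 30, 76.7% by the normal approximation) moves the result by less than one point.

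**Conclusion.** The concern holds. With 84 randomised and 30% dropout, about 59 patients complete, 5 short of 64. Completer power is about 76% (about 75% by t) against the stated 80%, a gap of about 4 points, or 8 randomised patients (84 against 92). This rests on a difference of 0.35, a residual SD of 0.5, a two-sided 0.05 test and equal dropout in the two arms.

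Power for the planned primary analysis is left open by the documents and could fall on either side of 80%. The HbA1c limits in 17.2 and 6.1 contradict each other, and the documents do not show which is intended. The size is modest, but the stated basis for the primary endpoint is wrong as written and should be corrected.

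**What to change.** Keep 84 and restate section 17.2 along these lines:

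> With 84 randomised and 30% dropout, about 29 patients per arm complete, giving about 76% power (normal approximation; about 75% by t) in completers for a difference of 0.35 at residual SD 0.5. Retaining 64 completers requires dropout of no more than about 24%. The primary analysis is intention to treat with last observation carried forward on all randomised patients, and its power depends on how much of the treatment effect dropouts retain.

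Put no power figure for the carried-forward analysis in the protocol, since any such figure would rest on assumptions that the documents do not support. Reconcile the HbA1c limit in 17.2 with the one in 6.1.

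The cost is wording. No patients are added and the analysis does not change. The stated power falls by about 4 points in completers, and the plan must acknowledge that this calculation does not fix the power of the primary test.

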18.0 Confidentiality

A. Confidentiality of Study Data#

Describe the local procedures for maintenance of confidentiality of **study data and any records that will be reviewed for data collection.**

18.1 A. Where and how will all data and records be stored? Include information about: password protection, encryption, physical controls, authorization of access, and separation of identifiers and data, as applicable. Include physical (e.g. paper) and electronic files.

Response: All patients' data records will be stored on password protected computers and or in locked cabinets within the research department. The research unit is locked after 5pm daily and all day on weekends. Identifiable patient information along with randomization information for each patient will be stored in locked cabinets in an locked archive room. This will only be accessible by study coordinator and the PI. Electronic data will be stored on password protected computers as coded data based on randomization number eg R-12 without any patients identifiable information attached. These electronic files will only be accessible by authorized study personnel.

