4.0 Study Design

4.1 Describe and explain the study design (e.g. case-control, cross-sectional, ethnographic, experimental, interventional, longitudinal, observational).

Response: This investigation will be a prospective, randomized, double blind, placebo controlled parallel design study conducted in patients with type 1 diabetes. The study will be conducted at Diabetes-Endocrinology Center of WNY, affiliated to the State University of New York at Buffalo.

84 overweight or obese patients with type 1 diabetes on treatment with either continuous subcutaneous insulin infusion (CSII; also known as insulin pump) or multiple (four or more) injections of insulin per day will be included in the study. They will be randomized into 2 groups of 42 patients each. The patients will be randomized to daily subcutaneous injections of placebo or liraglutide. In view of the possibility of hypoglycemia and the side effect of nausea all patients will be started on 0.6 mg of liraglutide per day. The dose will then be titrated up to 1.8 mg.

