19.0 Provisions to Monitor the Data to Ensure the Safety of Subjects

N/A: This study is not enrolling subjects, or is limited to records review procedures only. This section does not apply.

NOTE: Minimal risk studies may be required to monitor subject safety if the research procedures include procedures that present unique risks to subjects that require monitoring. Some examples include: exercising to exertion, or instruments

that elicit suicidality or substance abuse behavior. In such cases, N/A is not an acceptable response.

19.1 Describe the plan to periodically evaluate the data collected regarding both harms and benefits to determine whether subjects remain safe.

Response: The principal investigator [name], PhD and co-investigators [name] and [name] will review the data every 3 months to assess the safety of the participants. Furthermore they will also assess other risks including the physical, psychological, social, legal and economic harm to these patients. The investigators listed above will carefully watch for any invasion of privacy and breach of confidentiality. The principal investigator will be sharing the results of safety analysis of the study with the sponsor (JDRF) and to the IRB. The study groups will remain blinded. If there are any safety concerns then co-investigator [name] who is not directly involved with the patients and or in insulin titrations of the study participants will unblind the study groups on the discretion of principal investigator and the team will assess potential harm to the patients and inform the IRB and sponsor of this potential harm. The corrective actions will then be taken and research subjects will be withdrawn from the study if risks outweigh the benefits. The IRB will be kept well-informed at all times. During each patient visit, evolution of glucose levels (CGM) will be conducted to reduce the risk of hypoglycemia or hyperglycemia. After recruitment and completion of half of the target number of patients i.e. 42 patients, interim analysis will be performed to determine an overwhelming harms or benefits with one treatment option compared to another.

19.2 Describe what data are reviewed, including safety data, untoward events, and efficacy data.

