Response: Safety data will be reviewed every 3 months. Study endpoint data will be reviewed once after half of the recruited patients have completed the study and then at the end of the study

19.8 Describe the statistical tests for analyzing the safety data to determine whether harm is occurring.

Response: The statistical analysis will be carried out using student t-test, Chi-square and Wilcoxon's test for paired data

19.9 Describe any conditions that trigger an immediate suspension of the research.

Response:

- 1- New information about the safety of the used drug (Victoza) – liraglutide
- 2- Sponsor suspension of the funds.
- 3- Significant high incidence of SAE and events leading to withdrawal of subjects determined based on the continuous review by the investigators.

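### Safety unblinding and the half-way review are not walled off from staff who adjust insulin or remove participants, and the plan does not say who holds the arm code

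*Combined protocol and SAP*

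**What the plan says.** Section 4.1 describes a "prospective, randomized, double blind, placebo controlled parallel design study".

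**Safety review.** Sections 10.2, 19.1 and 19.6 have the principal investigator and co-investigators review safety every three months, and state: "The study groups will remain blinded". If a safety concern arises, one co-investigator "will unblind the study groups on the discretion of principal investigator and the team will assess potential harm to the patients". Sections 10.2 and 19.1 place that co-investigator outside patient contact and insulin titration; section 19.6 mentions only patient contact. The IRB and sponsor are then informed.

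**Half-way review.** Sections 10.2 and 19.1 plan an interim analysis once 42 patients have completed, looking for overwhelming harm or benefit of one treatment against the other. Section 19.7 adds: "Study endpoint data will be reviewed once after half of the recruited patients have completed the study". No analyst is named.

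**Insulin and withdrawal.** At week 1 in section 10.1, "Insulin dose will be adjusted at the discretion of the study investigator". Later visits adjust it as needed, and every visit after day 0 works to a common target of 70-180 mg/dl. Section 20.1 lets the principal investigator remove a participant for any reason thought appropriate.

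**Custody.** Section 18.1 A states: "Identifiable patient information along with randomization information for each patient will be stored in locked cabinets in an locked archive room". It continues: "This will only be accessible by study coordinator and the PI". Electronic files are held as "coded data based on randomization number eg R-12 without any patients identifiable information attached".

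**The concern.** Insulin is the co-intervention that acts most directly on HbA1c, the primary endpoint, and insulin dose is itself a secondary endpoint (section 2.1). Someone who titrates insulin and knows the arm can move both, even with a common glucose target, by how readily a dose is raised or cut. Someone who decides on removal and knows the arm can change which HbA1c values reach the analysis. HbA1c is a laboratory value, but that protects only its measurement. It does not protect against unequal co-treatment or unequal withdrawal.

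Bias of this kind enters the between-arm difference directly, and no analysis in section 17.1 can remove it. The protection has to lie in who sees what during the trial. The plan sets up part of that protection by using a separate co-investigator, and then passes the result on without restriction.

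**Working it through.** The plan states no figure on this point, so the check is a comparison of sections, followed by one labelled illustration.

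**Route 1: safety unblinding (10.2, 19.1, 19.6)**
- Default: groups stay blinded.
- Trigger: a safety concern, at the principal investigator's discretion.
- Unit unblinded: the study groups, not one patient.
- Who breaks the code: a co-investigator outside care and titration.
- Who then assesses harm: the team. The reviewers named in these sections are the principal investigator and co-investigators. No one who titrates or removes patients is excluded.

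The separation holds when the code is broken and ends when the result is passed on.

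**Route 2: half-way review (10.2, 19.1, 19.7)**
- This review is scheduled, not conditional.
- Comparing one treatment with the other needs data split by arm, at least as two coded groups.
- Coded labels may be easy to read. In the uncontrolled pilot (section 3.1, Table 2), basal plus bolus insulin fell from 26 + 25 = 51 to 13 + 15 = 28 units per day, a fall of 23/51 = 45%. If the trial shows anything similar, the insulin summary would identify the liraglutide group.
- Knowing which coded group is which does not by itself give a current patient's arm. It does so if the reader can also see which patients are in which group, and the plan does not say that this is hidden.
- Up to 84 - 42 = 42 patients would still be untreated or in treatment. This is an upper bound, since some will be partly through and some will have dropped out.

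**Route 3: custody (18.1 A)**
- If the stored information is the identity-to-R-number key, the blind is intact.
- If it includes the arm, two roles can read it, and one of them may remove participants (20.1).
- No section names a pharmacist, a sealed code or another holder of the allocation list. Section 11.2 says only that subjects receive a number and are randomised, and section 31.2 covers drug storage only.

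**How it would reach the primary result**
- Titration: insulin is adjusted throughout the 26 weeks (10.1).
- Withdrawal: HbA1c is scheduled at screening, week 12 and week 26 (10.1), with last observation carried forward (17.1). A patient removed before week 12 would contribute the screening value, that is, a change of zero.

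**Illustration only; the shift is assumed and has no source in the documents**
- Suppose knowledge of the arm shifts the HbA1c difference by 0.1 to 0.2 points among the later 42 of 84 patients.
- Overall shift: 42/84 × (0.1 to 0.2) = 0.05 to 0.10.
- Relative to the design difference of 0.35 (17.2): 0.05/0.35 = 14%; 0.10/0.35 = 29%.
- False-positive rate with no true effect, SD 0.5 (17.2), 42 per arm, two-sided 0.05 (sidedness assumed): SE = 0.5 × √(2/42) = 0.109; rate = 1 - Φ(1.96 - b/SE) + Φ(-1.96 - b/SE). For b = 0.05 this is about 7%, and for b = 0.10 about 15%.

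**The case against.** The strongest reply is that the plan already protects the blind. Groups stay blinded unless safety requires otherwise, and a person away from patients and titration breaks the code. Assigning that task to a separate person would make little sense if the principal investigator already held the arm list, so the stored information in section 18.1 is most naturally the identity-to-R-number key. The rest of the document also codes data and specimens by R-number (18.6, 30.1). Titration follows one glucose target in both arms, discretion is mentioned only at week 1, and nausea-related drops follow written steps.

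Much of this stands, and it rules out several stronger readings that a reader might infer:

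- **That the team is routinely unblinded.** Group unblinding is conditional on a safety concern.
- **That the principal investigator and coordinator hold the arm list.** Section 18.1 does not say so, and the number-only reading is at least as likely.
- **That these two people set insulin doses or grade nausea.** Section 10.1 refers only to the study investigator, and no section gives the coordinator either task.
- **That the half-way review reveals codes to the treating team.** It needs a split by arm, but the plan does not say who receives it.

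What the reply does not answer is the absence of any barrier after the code is broken or the half-way comparison is made. A common target narrows the room for unequal titration but does not close it, and the removal power in section 20.1 is broad.

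**Conclusion.** The concern holds as a gap in the plan, not as a demonstrated breach. Followed as written, the safety rule can reveal group allocation to investigators who may be adjusting insulin or removing participants. The half-way comparison has no named recipient outside the investigators. The custody wording in section 18.1 is ambiguous and needs one clarifying sentence.

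The documents give no basis for the size of any bias. A reader might take 14% to 29% of the design difference as an estimate; it is not one. It follows entirely from the assumed shift of 0.1 to 0.2 points and the upper bound of 42 patients. What can be said is that the direction is unpredictable, the bias could not be corrected afterwards, and the remedy is cheap enough to adopt without a size estimate.

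**What to change.** - **10.2, 19.1, 19.6 and 19.7:** the co-investigator already described as outside patient care and insulin titration holds the R-number-to-arm list, produces any by-arm safety or half-way comparison, and sends it to the IRB and sponsor. Only the resulting decision goes to the treating team. Use the same description of this role in all four places, since section 19.6 omits titration and section 19.7 names no one.
- **Same sections:** for a concern about one patient, break that patient's code only.
- **18.1 A:** define the stored randomisation information, and state that the principal investigator and coordinator hold only the identity-to-R-number link.

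The cost is protocol wording and, if the list is now elsewhere, moving it to a role that already exists. The three-monthly blinded safety review is unaffected. The small downside is that the treating team does not see by-arm data during the trial.
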